### 3. Prediction of Autoimmune Colitis

---

**Clustered genomic variants specific to patients who develop immune-related colitis after ipilimumab may predict this toxicity (Tarhini et al, submitted to ASCO 2014)**

Data generated in the context of UPCI 08-144 trial of neoadjuvant ipilimumab and funded by NIH award P50CA121973. These data have been submitted for presentation at the 2014 ASCO Annual Meeting (*Tarhini et al., Clustered genomic variants specific to patients who develop immune-related colitis after ipilimumab may predict this toxicity*). We identified a genomic signature to predict colitis predisposition among patients undergoing neoadjuvant ipilimumab therapy for locally/regionally advanced operable melanoma.

Rev. 3/15 **XIX.5 Tissue/Specimen Type**

1. Tumor tissue: Paraffin Block or Unstained Slides
2. Body fluids: Serum, Lymphocytes
3. Derivatives: DNA (genomic)

The project plans to test specimens from up to 1600 subjects depending on the availability of biospecimens. The tumor tissue blocks/slides are banked at the ECOG-ACRIN Central Biorepository and Pathology Facility. The research blood/blood products are banked at the ECOG-ACRIN Immune Monitoring and Cellular Products Laboratory (IMCPL) at the University of Pittsburgh Cancer Institute (UPCI).

1. Tumor: 15-17 (5 micron scrolls), or 15-17 (5 micron unstained slides); 70% tumor  
(Any extra tissue would be saved and returned to the ECOG-ACRIN Central Biorepository and Pathology Facility.)  
[These will be used for the testing of (1) gene expression profiling, (2) Immunohistochemistry, (3) activating mutations by targeted sequencing in select patients with unknown mutational status, (4) methylation status of DNA sequences]
  2. PBMC/Serum: 5 vials PBMC and 3 vials serum  
(An extra vial requested would be saved at the IMCPL and used only for unexpectedly low recoveries and running assays on different days.)
  3. DNA (genomic): one yellow top tube  
(Remaining specimen would be saved at the IMCPL.)  
[This will be used for the testing of genomic variants potentially predictive of autoimmune colitis induced by ipilimumab]
- 

**XIX.6 Laboratory Methods**

**1. Tumor Microenvironment**

General: These assays will be conducted at the UPCI Cancer Biomarkers Facility (CBF) Genomics Core (Director: [name]).

---

### 1.a. Baseline expression of immune-related pathways/genes

Microdissection of FFPE tumor specimens will be performed manually using an inverted microscope (Nikon Eclipse TE200) to obtain a minimum of 90% tumor cells for RNA purification. Dissection involves scraping cells from unstained sections of 5 micron thickness on slides aligned in register with serially cut hematoxylin and eosin stained specimens including tumor domains demarcated by a surgical pathologist. RNA purification will be performed using the Qiagen miRNeasy FFPE Kit and protocol (Qiagen, Valencia, CA) with isolated RNA suspended in nuclease-free water. Inclusion in subsequent *in vitro amplification* (IVT) assays is determined both by spectrophotometric absorption ratio [ $260/280 > 1.8$  (NanoDrop, Wilmington, DE)] and RIN values (RNA Integrity Index) determined via microchip electrophoretic analysis (Agilent Bioanalyzer 2100, Agilent Technologies, Santa Clara, CA). We have previously established that RIN values ranging from 5.0 to 8.0 in RNA from FFPE specimens can undergo successful *in vitro transcription* and amplification using a multiple primer approach. Amplification will be performed using the NuGen whole transcription method comprising the Ovation FFPE WTA assay (NuGEN, San Carlos, CA) employing random and 3' primers to eliminate amplification bias beginning with 100 ng total RNA. Confirmation of cDNA diversity will be obtained using the Bioanalyzer 2100 to generate an electrophoretogram for each amplification reaction regarding sample yield, integrity, and size diversity compared to a laboratory human RNA standard and a Universal Human Reference RNA (Stratagene, La Jolla, CA). Five micrograms of purified cDNA will be incubated with fragmentation buffer (NuGEN, San Carlos, CA) at 37°C for 30 minutes, then 95°C for 2 minutes. All cDNA samples will undergo hybridization on Affymetrix GeneChip HG U133A 2.0 arrays which contain overlapping probe sets for transcripts comprehensively representing the functionally characterized human genome. Briefly, fragmented cDNAs are mixed in a hybridization cocktail with water to a final volume of 220µl. 130ul of hybridization cocktail is hybridized on each array at 45°C for 18 hours. The arrays are then washed and stained with streptavidin-phycoerythrin in a GeneChip Fluidics Station 450 (Affymetrix) and scanned using a GeneChip Scanner 3000 (Affymetrix). Quality control (QC) parameters and expression intensity data are derived from the MAS 5.0 (Microarray Suite) and RMA algorithms (Robust Multi-array Average) of the Expression Console software (version 1.2.0.20; Affymetrix). Comparisons of global and individual gene expression data are performed using median normalized and log2 values transferred to Partek Genomics Suite v6.5 (Partek Inc, St Louis, MI). Statistical significance is performed at a false discovery rate (FDR) of less than 5% (q value) to control for Type 1 errors arising from multiple tests.

### 1.b. Tumor infiltrating lymphocytes and immunosuppressive markers (immunohistochemistry): CD3, CD4, CD8, FOXP3, PD-L1, IDO, CD45RO

Immunohistochemistry will be conducted at UPMC Shadyside Hospital, Department of Pathology, under supervision of [name] (E1609 Pathology Co-chair). Paraffin-embedded tissue sections (5 µm thick) will be scored at × 20 magnifications by a surgical pathologist ([name]) who will be blinded to patient and treatment status. Lymphocytes will be counted in 4 quadrants and added. The total numbers of intratumoral, peritumoral, and perivascular mononuclear cell infiltrates will be enumerated following standard immunohistochemical staining, as previously published, with FOXP3, CD4, CD8, IDO, PDL1 and CD45RO monoclonal antibodies.

## 2. Circulating Biomarkers

General: These assays will be conducted at UPCI Immune Monitoring and Cellular Products Laboratory (IMCPL; Director: [name]) which is CAP accredited and CLIA certified. All assays are run according to SOPs by trained and competency tested personnel, and include healthy donor controls. The laboratory participates in external proficiency panels for flow cytometry and Luminex.

### **2.a. Circulating Cellular Populations**

Absolute lymphocyte count will be determined by the hospital clinical lab by standard procedures and is being collected prospectively on study-specific forms. All other cellular assays will be tested by flow cytometry in the IMCPL, according to existing SOPs. The flow cytometer (FC500) is QC'd daily and monitored for any change in laser function. All antibodies are tested before use in patient material testing.

Cellular subpopulations are sequentially gated on, and both MFI and % positive is reported. Dot plots and histograms are reviewed by an experienced supervisor and results inserted in spreadsheets which are sent to the project associated biostatistician. Negative populations are identified by isotype antibodies or negative control cells or unstimulated cells (depending on assay or antibody). Any cell populations with any degree of positive marker expression are listed by the specific MFI or % positive value.

### **2.b. Circulating Serum Proteins**

Most serum proteins will be analyzed by the multiplex Luminex assay, and analyzed on a BioRad reader. Concentrations are automatically determined based on kit standard curves from the software. Additional controls include R&D Systems Multiplex QC controls which are mixed cytokines with expected yield values. Large projects use a single lot of kits whenever possible. Analytes requiring non-standard dilutions (like CRP) are run singly. Analytes not compatible with multiplexing are run singly in ELISA format kits. Results are presented as the pg/ml values reported and results above or below the limits of detection are reported as such. Given the broad range of detection for the Luminex platform, values below the LLD are generally considered negative, and values above the ULD are either considered statistically as equal to the ULD, or, if a reasonable fraction of samples are over the ULD, those samples are diluted further and re-run.

## **3. Prediction of Autoimmune Colitis**

### **3.a. Targeted Deep Sequencing to identify genomic variants specific to patients who develop immune-related colitis after ipilimumab therapy.**

General: These assays will be conducted at the UPCI Cancer Biomarkers Facility (CBF) Genomics Core (Director: [name]).

We identified a genomic signature to predict colitis predisposition among patients undergoing neoadjuvant ipilimumab therapy for advanced melanoma (*Tarhini et al., Clustered genomic variants specific to patients who develop immune-related colitis after ipilimumab may predict this toxicity. Submitted to the 2014 ASCO Annual Meeting*). The proposed study will extend these findings in a larger patient cohort. Targeted, deep sequencing will focus on a customized 10 gene/9 SNP panel developed in our laboratory. PBMC (blood) samples ( $1 \times 10^6$  cells) will be extracted using the QIAamp DNA Micro kit (Qiagen, Valencia, CA) and DNA obtained by column purification will undergo QC to identify samples ( $>100$  ng/ul) with OD 260/280  $>1.8$  (Nanodrop ND-1000 spectrophotometer, NanoDrop, Wilmington, DE) and fragments  $\geq 300$  base pairs (Bioanalyzer 2100: 12000 DNA Chip, Agilent Technologies, Santa Clara, CA) for library

construction. Primers for target genes will be used to generate amplicon libraries via PCR selection (Perkin Elmer 9700, Bridgeville, PA) (99°C x 2min, 15 cycles at 99°C x 15 sec, 60°C x 8 min, 10°C x hold) followed by enzymatic digestion and phosphorylation of the multiplexed amplicons. The amplicons are then indexed (Ion Xpress Barcode Adapters, Life Technologies, Grand Island, NY) and adapters ligated for attachment to Ion Spheres (ISP) in micro-reactors for clonal amplification using emulsion PCR (One Touch 2 instrument; 60 cycles, PGM 200bp kit v2). Templated ISPs are recovered and enriched using biotin labeled primers bound to streptavidin coated metallic beads (DynaBeads C1, Life Technologies). The ISPs are then washed, stripped from the streptavidin beads (125mM NaOH; 0.1% Tween 20) and sequencing is performed on the Ion Torrent Personal Genome Machine (PGM) using the 200bp sequencing kit v.2 and a washed, precalibrated semiconductor chip (318v.1 for 200bp libraries, Life Technologies) on the PGM platform. Sequencing comprising 500 flows (125 washes of each of 4 nucleotides) has provided 1000 x base depth of parsed barcoded reads aligned to Human Reference Genome HG19 on 10 samples undergoing simultaneous sequencing. BAM files (binary format), linked BAI files (indexed files) and variant call files (vcf) (Torrent Suite 4.0) are transferred from the Ion Torrent server (Dell Precision T7500, Intel Xeon Quad Core 2.93GHz, Ubuntu 10.04) to the analysis server (MacPro 5.1, Intel Xeon 6 Core 2.4GHz, OSX 10.8.4; GenomOncology Inc., Westlake, OH). A Galaxy Project plug-in (Pennsylvania State University, State College, PA) generates additional vcfs and INDELS using GATK (Genome Analysis Toolkit; UnifiedGenotyper v. 2.3), SAMtools (mpileup v. 0.1.18) and a manual variant caller algorithm (variant:  $\geq 5\%$  base calls differ from HG19 with  $\geq 300$  calls at Phred Score=20 or  $p < 0.01$ ). All variants and INDELS are validated by manual curation of the BAM file sequence using the Integrated Genomics Viewer (IGV Broad Institute). All patient samples will be compared for commonality of single nucleotide variants and INDELS based on colitis symptoms.

**XIX.8 Statistical Design**

**Endpoints (outcomes)**

The clinical endpoints are relapse free survival (RFS) and overall survival (OS). RFS is defined as the time from study entry to relapse or death, whichever happens first. OS is defined as the time from study entry to death.

**Primary Comparison**

The primary objective of the study is to build a prognostic model using the candidate biomarkers for each study arm. The secondary objectives are (a) to test for the therapeutic predictive power of prognostic panels discovered; (b) to search for

therapeutic predictive markers to guide the therapeutic choice of either ipilimumab or HDI; (c) to test for association of pre-specified genetic variants and the occurrence of colitis.

### **Case Selection**

We plan to include all subjects accrued in E1609 ipilimumab study arms (A, D and C, F) and HDI study arm. Arms A and D treat patients with high dose ipilimumab (HIP), arms B and E with HDI and arms C and F with low dose ipilimumab (LIP).

### **Power Justification**

The target accrual for E1609, which was activated in May 2011, is 1600 (600 HDI, 500 HIP, 500 LIP), which will be completed by August 2014. Thus, by 2015, we will have at least 1 year of follow-up data for each patient in the trial for analysis and validation of potential biomarkers and the development of prediction models for RFS and OS of the patients in each treatment arm.

We currently estimate that biospecimens are available for testing from approximately 80% of subjects enrolled on E1609. We expect that these numbers will improve as we continue to follow up with participating sites on biospecimen submission.

### **Power for Primary Objective: Prognostic Modeling**

Subjects will be divided into a training set and a validation set (250 each for the LIP and HIP groups, 300 for HDI group). Here we demonstrate our power in the development of a prognosis model in one of the ipilimumab arms. We base our power calculation on a test that compares the SN and SP simultaneously. Following the E1609 protocol, we expect that the cure rate for the ipilimumab arm will be 40% and the median RFS for the uncured patients is 0.48 years. As described above, we expect to obtain samples from  $\geq 80\%$  of the patients, after accounting for 95% assay success rate, we will have about 76 cases (patients who had event within 1 year) and 114 controls (patients who are followed up for 1 year without any event). We define a minimal useful model to be one with a sensitivity of 75% or higher and a specificity of 75% or higher. If the true sensitivity and specificity are 89% and 87% for our model, we will have over 80% power to claim that our model is significantly better than the minimal useful model ( $\alpha=0.05$ ).

### **Power for Predictive Modeling**

With limited preliminary data, predictive modeling is our secondary objective. Nevertheless, here we estimate our power for validation of a predictive biomarker in the validation set. We base our calculation on the analysis of one of the ipilimumab arms (HIP or LIP) and the HDI arm. However, it is very likely that the RFS profiles are very similar between the two ipilimumab arms. If this turned out to be the case by the time we analyze the data, we will consider combining the data of these two arms. Thus, our power estimate here is a conservative estimate. The goal here is to determine whether there is a significant difference between the clinical benefits of patients in different marker strata. That is, we are testing the interaction of the dichotomized marker value (we discuss how to dichotomize the marker value in details in our analysis plan in the following section) and the treatment group. We calculate our power based on the method by Peterson and George. As shown in Table 1, with 418 samples total, we will be able to detect an interaction term with HR between 1.9-2.1 assuming the marker stratum 1 proportion is between 50-70% with a two-sided test ( $\alpha=0.01$ ). Details on the power calculation for the predictive modeling is given below.

Table 1 Power calculation for test of interaction ( $\alpha = 0.01$ , two-sided)

Marker stratum 1 Freq. ( $g_j$ )	$f_{11}$	$f_{12}$	$f_{21}$	$f_{22}$	$\lambda_{11}$	$\lambda_{12}$	$\lambda_{21}$	$\lambda_{22}$	$\Delta_1$	$\Delta_2$	$\Delta$	Power
0.5	0.273	0.273	0.227	0.227	1.1	0.734	0.6	0.776	1.833	0.946	1.938	0.69
					1	0.834	0.5	0.876	2	0.952	2.101	0.8
					1.15	0.684	0.6	0.776	1.917	0.881	2.174	0.84
					1.05	0.784	0.5	0.876	2.1	0.895	2.346	0.91
					1.15	0.684	0.55	0.826	2.091	0.828	2.525	0.95
					1.2	0.634	0.5	0.876	2.4	0.724	3.316	1
0.6	0.327	0.218	0.273	0.182	1.05	0.718	0.6	0.82	1.75	0.875	2	0.72
					1	0.793	0.55	0.895	1.818	0.885	2.053	0.76
					0.95	0.868	0.5	0.97	1.9	0.894	2.124	0.8
					1	0.793	0.5	0.97	2	0.817	2.448	0.93
					1.1	0.643	0.5	0.97	2.2	0.662	3.321	1
					1	0.723	0.6	0.893	1.667	0.81	2.058	0.69
0.7	0.382	0.164	0.318	0.136	1.2	0.257	0.8	0.427	1.5	0.602	2.494	0.79
					1	0.723	0.55	1.01	1.818	0.716	2.539	0.92
					1.15	0.373	0.7	0.66	1.643	0.566	2.904	0.95
					1.05	0.607	0.5	1.127	2.1	0.538	3.9	1

### XIX.9 Statistical Analysis Plan

- Statistical methods for the main analyses: For the single marker association with PFS and OS, Cox proportional hazards (CoxPH) regression will be used. Because some long-term cures have been observed in patients with stages IIB – III melanoma treated with HDI and ipilimumab, we will also perform exploratory analyses using a cure-rate model for RFS as a supplement to the CoxPH regression analyses proposed above. For multi-marker prognostic model, both the Lasso Cox proportional hazard regression and the Cox proportional hazard regression will be used. And the results will be compared.
- Transformations applied to variables: Distribution of data of different types will be checked and appropriate transformation will be used when necessary.
- Methods for marker cutpoint determination: For the predictive biomarker, we will follow the recommendation of Janes et al 2013 and use the marker-by-treatment predictiveness curves to guide the dichotomization of the marker (or risk score for multi-marker panel). Specifically, we will dichotomize the marker (or score) around the point where the two predictive curves cross.

- Variable selection procedures: We will use two strategies and compare our results: Cox proportional hazard regression with forward regression and Lasso Cox proportional hazard regression.
- List of standard clinical variables to be incorporated into models or other analyses: Clinical variables that we will consider to be included in the models are age, sex, Breslow thickness, recurrent disease at study entry, ulceration of the primary tumor, lymph-node status, number of positive lymph nodes, completion of lymph node dissection prior to treatment, microscopic extranodal extension, and mitotic rate in the primary tumor.
- Multiple-comparisons adjustment methods: To adjust for the multiple testing, the Benjamini and Hochberg's (BH) method will be used to control the false-discovery rate (FDR) at 5% for all candidate marker analyses. For the whole genome scan, we will use the procedure described in Storey 2002 to control the FDR at 5%.
- For complex studies, methods that will be used to validate the analysis results, or a rationale for not performing a validation study: Given the uniqueness of this study population, we do not a compatible independent validation cohort, but our study population is large enough that we will randomly split the samples into two groups of equal size, using one of them as the **training set** and the other one as the **validation set**. However, to avoid over fitting, the validation set will be held out till the last stage of the study, where it will be used to validate the final models.
- Any other information necessary for the Committee to understand and evaluate the main analyses you are proposing: The detailed analysis plan for our primary objectives is included below.

### Secondary Objectives

For the predictive biomarker analysis, again we will randomly split the samples into two groups of equal size, using one of them as the training set and the other one as the validation set. However, to avoid over fitting, the validation set will be held out till the last stage of the study, where it will be used to validate the few (<=5) final biomarkers (or panels).

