#### **XIX.2 Objectives**

1. Primary Objective: Generating prognostic biomarker signature for patients treated with Ipilimumab and high dose IFN $\alpha$  (HDI).
  - a. Aim 1: Testing of specific circulating biomarkers of therapeutically predictive value generated by significant preliminary data
    - i Cellular populations: (1) absolute lymphocyte count; (2) T regulatory (CD4+CD25hi+Foxp3+, CD4+CD25hi+CD39+) and MDSC (monocyte gate HLA-DR+ low/CD14+, monocyte gate Lin1-/HLA-DR-/CD33+/CD11b+, lymphoid gate Lin1-/HLA-DR-/CD33+/CD11b+); (3) IFN $\gamma$ +CD4+ and IFN $\gamma$ +CD8+ antigen specific T cells (gp-100, MART-1, NY-ESO-1 peptides); (4) CD4+ and CD8+ ICOS-hi T cells; (5) IFN $\gamma$ +CD8+CXCR3+VLA4+ T cells
    - ii Serum proteins: CRP, LDH, S100, MIA, YKL40, IL1 $\alpha$ , IL1 $\beta$ , IL2, IL2R $\alpha$ , IL6, IL8, IL10, IL17, IL12p40, TNF $\alpha$ , IFN $\alpha$ , MIP1 $\alpha$ , MIP1 $\beta$ , TNF-RII, TGF- $\alpha$ , TIMP-1, CXCL10 (IP10), CXCL11, CXCL9, VEGF
  - b. Aim 2: Testing of specific biomarkers within the tumor microenvironment (TME) of therapeutically predictive value generated by significant preliminary data
    - i Expression levels of immune related-genes (RNA microarray): CCL2, CCL3, CCL4, CCL5, CD8A, CXCL10, CXCL11, CXCL9, IDO, PRF1, GZMB, HLA-DMA, HLA-DOA, CD79B, IGH, IGKC, IGLC1, HLA-DQA1, IGHM, CD79A, IGHD, CD3G, CD3D, HLA-DPA1, LAT, VAV1, INPP5D, IL2RB, IGHG1, CIITA, IL21R, STAT1

- ii Tumor infiltrating lymphocytes and immunosuppressive markers (immunohistochemistry): CD3, CD4, CD8, FOXP3, PD-L1, IDO, CD45RO

Using known clinical covariates and the markers identified in Aims 1 and 2, we will use the entire data set to develop and validate models capable of identifying which patients belong to different prognostic groups.

2. Secondary Objectives:

- a. Testing the therapeutic predictive value in relation to ipilimumab of the prognostic biomarker signature identified in the primary objective.

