### Searching for predictive biomarkers

Based on our and others studies, we have defined a pool of candidate prognostic biomarkers. We expect that some of these markers are also predictive. Thus, we would consider these markers as our top tier candidate predictive markers. First, we will follow the recommendation by Janes et al, and use the marker-by-treatment predictive curves using 1-year PFS (or 1-year OS) as the "response rates" to evaluate the interaction between the marker and the treatment. Only the markers with a qualitative interaction with the treatment will be further investigated, since they are the only markers that could guide the choice of treatments. We will dichotomize marker around the point where the two predictive curves cross. To test the interaction between the marker and treatment, we will fit the Cox proportional hazard model of the following form:  $\lambda(t) = \lambda_0(t) \times \exp\{\beta_1 Md + \beta_2 T + \beta_3 T * Md + \sum \beta_i \text{Covariates}\}$ , where Md denotes dichotomized marker value, T denotes treatment (HDI/HIP/LIP), the function  $\lambda(t)$  represents the event rate at time t, and  $\lambda_0(t)$  represents the corresponding baseline event rate. Likelihood ratio test will be used to test the null hypothesis of  $\beta_3=0$ . To adjust for the multiple testing, the Benjamini and Hochberg's (BH) method will be used to control the false-discovery rate (FDR) at 5%. We may also consider the risk score from the prognostic models developed above as a continuous marker and analyze them in the same way as described above. Markers (and risk scores) that show a significant qualitative interaction with the treatment effect will be further ordered by the estimated 1-year RFS (or OS) rate under the marker-policy. The top few (<5) predictive biomarkers may be validated in the

validation set. Given the lack of preliminary data on predictive biomarkers, if our search among the top tier markers failed, we will consider a genomic scan of gene expression to search for potential predictive biomarkers using the same strategy described above in the training dataset.

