We will also consider building a multi-marker prediction model. Given the limited sample size, we will consider only the top 3-5 markers in the model. We will first fit a CoxPH model with main effects of the markers and the clinical factors:  $\lambda(t) = \lambda_0(t) \times \exp\{\sum \beta_i M + \sum \beta_i \text{Covariates}\}$ , and test the predictive value of the predicted risk score (the linear combination of this model) as described above.

The top few ( $\leq 5$ ) predictive markers (and/or panels) will be validated in the validation set. The same cutoff point will be used to dichotomize the marker value (or risk score value). CoxPH models with interaction term between the dichotomized marker and the treatment will be fitted. We will compare the direction and magnitude of the interaction term to that obtained in the training set. Likelihood ratio tests will be used to test the interaction of each marker and the treatment effects. A p-value of 0.01 (0.05/5) will be considered statistically significant.

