**Development and validation of the prediction model.** The model development will be carried out at two levels: within each Aim (i.e., using markers within the same category) and across Aims (using markers that are discovered in all Aims). The main goal is to develop a prognosis model of RFS in the HIP and LIP arms. However, we will also take the advantage of the availability of the HDI arm to develop a prognosis model for melanoma patients treated with HDI. Therefore, we will develop a prognosis model for each arm of the study. Given the uniqueness of this study population, we do not have a compatible independent validation cohort, *but our study population is large enough that we will randomly split the samples into two groups of equal size, using one of them as the **training set** and the other one as the **validation set**. However, to avoid over fitting, the validation set will be held out till the last stage of the study, where it will be used to validate the final models. The small model within each subgroup of the biomarkers will be evaluated through cross-validation within the training set.*

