We will first use the Lasso Cox proportional hazard regression (LPHR) to develop a prognosis model for RFS using the training set. The Lasso was developed by Tibshirani 1996 and uses an  $l_1$  penalty to achieve a sparse solution, which allows simultaneous variable selection while fitting the model. This method has been applied to generalized linear regression and CoxPH models. Friedman et al. developed a fast algorithm for these methods and implemented it in a user-friendly R package, glmnet. Lasso has attracted more and more attention on the analysis of high-dimensional data because of its capability to perform the regression with outstanding accuracy in a large feature space, while simultaneously selecting the features. The tuning parameter will be trained through ten-fold (10x) cross validation within the training set. The linear combination score of the resulting model will be used to classify the patients into low-, intermediate-, and high-risk groups (cutoff at the 33% and 67% percentiles of the score). Hazard ratios (HRs) between the groups will be calculated. Log rank tests will be used to compare the RFS among these groups. The ability of this score to predict 1-year RFS will be evaluated using a time-dependent ROC curve. The area under the ROC curve (AUROC) will be calculated. An optimal cutoff point, which produces the best prediction (highest accuracy), will be chosen, and the corresponding sensitivity (SN), specificity (SP), and accuracy will be reported. The moderate number of candidate markers considered in each aim and the relatively large number of samples also enables us to use the regular CoxPH regression as a complement method to the LPHR. Markers will be evaluated for inclusion in the CoxPH model by forward stepwise selection. We will follow the same approach described above to evaluate the predictability of the model. Several popular machine-learning methods have been extended to handle right-censored data and predict subject survival status *at a specific time point*. We will use these methods as alternative methods to predict 1-year RFS for these patients and compare the performance of these methods to the LPHR model and Cox regression model. Specifically, univariate Cox regression will be used to evaluate the association of each individual marker and RFS. The BH method will be used to control the FDR at 5%. We will apply the random survival forest and the survival SVM to markers that passed the univariate analysis to generate a prognostic model to predict 1-year RFS. We will also use a bootstrap method in combination with the machine learning algorithm in marker selection. We will cross check the results of both methods for consistencies. The SN, SP, and accuracy will be calculated for each model and compared by McNemar tests between each pair of models. To avoid over fitting of the data, 10x cross validation within the training set will be used. In addition, ***the final models will be validated in the validation set.*** Specifically, the model parameters estimated using the training data will be applied to the validation set. For the survival model, the HR low-, intermediate-, and high-risk

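### Nothing ties the predictive-biomarker split to the prognostic split or keeps a score's training patients out of its validation, so the 0.01 level may fail for the arm-specific risk scores

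*Combined protocol and SAP*

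**What the plan says.** XIX.9 Statistical Analysis Plan and the Detailed Analysis Plan for the Primary Objective randomly halve the samples into training and validation sets. The model is fitted on the first half: "We will first use the Lasso Cox proportional hazard regression (LPHR) to develop a prognosis model for RFS using the training set". Fitting is separate by arm: "we will develop a prognosis model for each arm of the study". The other half is reserved: "the validation set will be held out till the last stage of the study, where it will be used to validate the final models".

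Under Secondary Objectives, the predictive analysis gets its own splitting sentence: "For the predictive biomarker analysis, again we will randomly split the samples into two groups of equal size". The validation half described there serves a different purpose, which is to confirm at most five final biomarkers or panels.

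The fitted scores are carried into this second analysis. XIX.2 lists as secondary objective (a): "Testing the therapeutic predictive value in relation to ipilimumab of the prognostic biomarker signature identified in the primary objective". Searching for predictive biomarkers adds: "We may also consider the risk score from the prognostic models developed above as a continuous marker". Each candidate taken forward is tested for interaction with treatment in the validation set: "A p-value of 0.01 (0.05/5) will be considered statistically significant".

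**The concern.** A score fitted in one arm has two parts: real prognostic signal, which should act in both arms, and overfitting, which predicts outcome only in the patients who trained it. Those patients are all in one arm. If some of them reappear in the validation set, the score looks stronger in that arm than in the comparator. A treatment-by-score test reads that difference as a predictive effect.

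At stake is a score declared useful for choosing between ipilimumab and HDI when it has no such value. XIX.9 says that no compatible independent cohort exists, so the internal hold-out is the only safeguard before such a claim.

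**Working it through.** **The plan's own figures.** Power Calculation for Predictive Modeling gives 250 ipilimumab and 300 HDI patients, 80% sample availability and 95% assay success: N = 550 × 0.80 × 0.95 = 418, as stated. That is 190 ipilimumab and 228 HDI patients.

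Power = Φ(√(N (log Δ)² / Σ 1/(e_ij f_ij)) − z_0.995), where e = 1 − [exp(−λF) − exp(−λ(A+F))]/(λA), A = 3.3 and F = 1. (The plan prints Φ⁻¹; the table values follow from Φ.) For the row with a 50% marker stratum and Δ = 2.101, the event probabilities are 0.893, 0.852, 0.703 and 0.864, and Σ 1/(e f) = 19.76. The square root is √(418 × 0.551/19.76) = 3.41, and Φ(3.41 − 2.576) = 0.799 against the stated 0.80. All 16 rows of Table 1 reproduce to within 2 points. The power calculation is sound on its own terms; the question is the level of the test.

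**Overlap if a second, independent half-split is drawn.** A held-out patient in the score's own arm was in the first training half with probability 0.5.

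- Ipilimumab score: 0.5 × 190 = 95 patients; 95/418 = 22.7% of the two-arm validation set.
- HDI score: 0.5 × 228 = 114 patients; 114/418 = 27.3%.
- Ipilimumab score in a three-arm validation set: 95/(190 + 190 + 228) = 15.6%.

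**Effect on the test.** The documents give no false-positive rate, so it was simulated with no true interaction, 2,000 trials per scenario. Taken from the plan: 380 ipilimumab and 456 HDI patients with usable samples (500 and 600 × 0.76), hazards 0.688 and 0.917, 3.3 years' accrual, one year's minimum follow-up, and a two-sided likelihood-ratio test at 0.01. Assumed: 25 or 75 independent candidates (XIX.2 lists roughly 75), none or five truly prognostic (log HR 0.2 in both arms), forward-stepwise Cox with entry at p < 0.05 fitted in the ipilimumab training half, and at most 5 or 10 markers kept.

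| Candidates | Prognostic | Max kept | Cut | One split | Second split |
|---|---|---|---|---|---|
| 75 | 0 | 10 | median | 0.6% | 13.0% |
| 75 | 5 | 10 | median | 1.1% | 8.2% |
| 75 | 5 | 10 | curve crossing | 1.1% | 7.8% |
| 25 | 0 | 10 | median | 0.9% | 3.6% |
| 25 | 5 | 5 | median | 0.7% | 2.7% |

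Simulation error is about 0.2 points at 1% and 0.8 points at 13%. A single unfitted marker under a second split gave 0.5% to 1.3%.

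**With Lasso, the plan's first method.** These runs used ten-fold cross-validation, 75 candidates and cure-model RFS.

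- Median cut, 400 runs per scenario, runs that kept no marker counted as non-rejections: second-split rates of 3.5% (no prognostic markers), 5.8% (five at log HR 0.2) and 2.5% (five at log HR 0.3). Among runs that kept a marker: 9.0%, 7.8% and 2.6%, against 0.6%, 0.7% and 1.3% on one split.
- A separate set of about 1,300 runs per scenario gave 5.5% before screening for pure-noise markers; Lasso kept no marker in about 60% to 63% of those runs. Adding the crossing-point cut and the plan's screen (a qualitative interaction in training, with p < 0.05 standing in for the Benjamini-Hochberg rule, and the same direction in validation) gave an end-to-end false-validation rate of 1.4% with noise and 1.5% with five prognostic markers. One split gave 0% to 0.2%. Among scores that passed the screen, the validation test still rejected in about 10% to 15%.

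**Screening inside the training set.** When a fitted score is tested for interaction in the patients who trained it, the 0.01 test rejected in 47%, 32% and 17% of the 400-run Lasso scenarios. This affects which candidates advance. On one fixed split it does not disturb the level of the final test.

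**The case against.** The strongest reply is that a second draw is only inferred. The sentence nearly repeats the earlier splitting sentences, and a redraw would move about half of the first validation set into the second training set, against the promise to hold it until the last stage. The power sections also read as if one validation set of 250, 250 and 300 serves both purposes. This stands: the text is ambiguous, and one split may be intended. But nothing says so, and the literal procedure is a fresh random split with its own training and validation sets.

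A second reply is that testing the score is optional. The wording under Searching for predictive biomarkers is permissive. XIX.2 and the Primary Comparison text in XIX.8, however, list testing the prognostic signature or panels as the first secondary objective.

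Three stronger inferences are tempting and do not hold:

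- *Half of all held-out patients trained the score.* That is true only within the score's own arm.
- *The 0.01 level fails for the whole predictive analysis.* Single markers carry no fitted weights and keep about 1%. The multi-marker score under Searching for predictive biomarkers is fitted without arm-specific terms and lacks this mechanism.
- *A noise score would be validated more than one time in ten.* Rates that high come from unshrunken selection without the training-set screen, and the plan specifies both Lasso and a screen. A noise score would also be expected to fail the prognostic validation, although the plan does not say that this check comes first.

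**Conclusion.** The concern holds for the arm-specific risk scores, conditional on a second split. The unscreened interaction test then rejects in roughly 3% to 13% of null trials at a nominal 1%, depending on the number of markers and the selection method. With Lasso and the screen, the end-to-end rate falls to about 1.5%. The right comparison for that figure is the 0% to 0.2% from one split, not 1%, because the screen alone removes most null scores.

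The direction does not depend on the modelling choices tried; the size does. The runs assume independent markers, no covariates and stand-ins for the exact screening rule. If the same split was intended, the final test holds its level and only the wording needs correcting. The matter is confined to a secondary objective of a banked-specimen appendix: no co-primary endpoint, trial alpha or patient decision in E1609 is affected. It should still be corrected, because the procedure as written can invalidate the only validation available.

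**What to change.** In XIX.9, Secondary Objectives, replace the splitting sentence with a statement that the single training/validation split made for the primary objective, stratified by arm, is used unchanged for all prognostic and predictive analyses. Test each locked score and cut-off once, in the untouched validation half.

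Under Searching for predictive biomarkers, add that an arm-specific fitted score screened for interaction in the training set is represented by its cross-validated (out-of-fold) values. This improves which candidates advance; it is not needed for the level of the final test once there is one split.

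The cost is two sentences and out-of-fold scores in the code. No samples are added, and N = 418 and the stated power do not change. In the stepwise simulations one split returned the test to 0.6% to 1.1%.
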